9.2 Secondary Pharmacokinetic Analyses

9.2.1 Endpoint / Variables

9.2.1.1 Drug Concentration Measures

Refer to Appendix 5: Data Display Standards & Handling Conventions (Section 14.5.3 Reporting Standards for Pharmacokinetic)

9.2.1.2 Derived Pharmacokinetic Parameters

Pharmacokinetic parameters will be calculated by standard non-compartmental analysis according to current working practices and using the currently supported version of WinNonlin. All calculations of non-compartmental parameters will be based on actual sampling times. Pharmacokinetic parameters listed will be determined from the plasma concentration-time data, as data permits.

Part 1:

Parameter	Parameter Description
AUC(0-t)	Area under the concentration-time curve from zero up to the last quantifiable concentration will be calculated using the linear trapezoidal rule for each incremental trapezoid and the log trapezoidal rule for each decremental trapezoid
tmax	Time to reach Cmax, determined directly from the concentration-time data.
tlag	Lag-time (time delay between drug administration and first observed concentration)
t½	Apparent terminal half-life will be calculated as: t½ = ln2 / lambda_z
tlast	Time of last quantifiable concentration, determined directly from the concentration-time data.
C24	Observed concentration 24 hours post-dose, determined directly from the concentration-time data.

NOTES:

- Additional parameters may be included as required.
- Lambda_z is the terminal phase rate constant.

Part 2

Parameter	Parameter Description
Ctrough	Observed pre-dose concentrations on Days 2 to 11, determined directly from the concentration-time data
Ro[AUC(0-τ)]	Accumulation ratio based on AUC(0- τ), determined by; Day 11 AUC(0- τ) / Day 1 AUC(0- τ)
R(Cmax)	Accumulation ratio based on Cmax, determined by; Day 11 Cmax / Day 1 Cmax
R(Cτ)	Accumulation ratio based on $C\tau$, determined by; Day 11 $C\tau$ / Day 1 $C\tau$

NOTES:

- Additional parameters may be included as required.
- Cτ, and Ctrough will be extracted from the concentration data by Clinical Statistics group and merged with other calculated PK parameters provided by CPMS.

All the derived parameters described above will be listed. For each of these parameters, except tmax and tlag, the following summary statistics will be calculated for each treatment group: n, arithmetic mean, standard deviation (SD), median, minimum, maximum, geometric mean with associated 90% CI, standard deviation of logarithmically transformed data, and the between-participant CV (%CVb) based on the geometric mean for the loge-transformed PK parameters. For tmax and tlag, median, maximum, minimum, arithmetic mean and standard deviation will be calculated.

9.2.2 Summary Measure

The measures used for the treatment comparisons are the followings:

- For part 1; Not applicable.
- For part 2; Accumulation ratios: Ro[AUC(0- τ)], R(Cmax), R(C τ).

9.2.3 Population of Interest

The secondary pharmacokinetic analyses will be based on the Pharmacokinetic population, unless otherwise specified.

9.2.4 Strategy for Intercurrent (Post-Randomization) Events

Not applicable.

9.2.5 Statistical Analyses / Methods

Details of the planned displays are provided in Appendix 12: List of Data Displays and will be based on GSK Data Standards and statistical principles.

Unless otherwise specified, endpoints / variables defined in Section 9.2.1 will be summarised using descriptive statistics, graphically presented (where appropriate) and listed.

Statistical Methodology Specification

Part 2 Steady State Assessments

Endpoint / Variables

GSK2838232 pre-dose values between Days 2 through 11

Model Specification

• Achievement of plasma GSK2838232 steady-state will be assessed by calculating the 90% CI of the slope of the linear regression of $\log_e(C\tau)$ versus time. The dependent variable in the mixed effect model will be $\log_e(C\tau)$ and the model will include a random intercept effect for participant and a fixed slope effect for study day. Day will be treated as a continuous variable in the model.

Model Checking & Diagnostics

- Model assumptions will be applied, but appropriate adjustments may be made based on the data.
- The Kenward and Roger method for approximating the denominator degrees of freedom and correcting for bias in the estimated variance-covariance of the fixed effects will be used.
- An unstructured covariance structure for the R matrix will be used by specifying 'type=UN' on the REPEATED line.
- In the event that this model fails to converge, alternative correlation structures may be considered such as CSH or CS.
- Akaike's Information Criteria (AIC) will be used to assist with the selection of covariance structure.
- Normality assumptions underlying the model used for analysis will be examined by obtaining a
 normal probability plot of the residuals and a plot of the residuals versus the fitted values (i.e.
 checking the normality assumption and constant variance assumption of the model
 respectively) to gain confidence that the model assumptions are reasonable.
- If there are any departures from the distributional assumptions, alternative models will be explored using appropriate transformed data.

Model Results Presentation

- Steady state will be reached if the pre-dose concentration slope estimate is close to zero or the 90% CI for the slope estimate includes zero.
- Mean plasma GSK2838232 pre-dose values between Days 2 through 11 and C_{τ} of Day 11 will be plotted against time on linear and semi-logarithmic scale..

Subgroup Analyses

Not applicable

Sensitivity and Supportive Analyses

Not applicable

Part 2 Accumulation

Endpoint / Variables

AUC(0-τ), Cmax and Cτ between Day 11 and Day 1

Model Specification

• The extent of accumulation of GSK2838232 will be evaluated by comparing AUC(0- τ), Cmax and C τ between Day 11 and Day 1. For each of these comparisons an analysis of variance will be conducted on the log scale. The difference between Day 11 and Day 1 least square (LS) means and a 90% CI will be computed by fitting a mixed effects model with the log-transformed PK parameter as the dependent variable, day as a fixed effect and participant as a random effect.

Model Checking & Diagnostics

- Model assumptions will be applied, but appropriate adjustments may be made based on the data
- The Kenward and Roger method for approximating the denominator degrees of freedom and correcting for bias in the estimated variance-covariance of the fixed effects will be used.
- Normality assumptions underlying the model used for analysis will be examined by obtaining a
 normal probability plot of the residuals and a plot of the residuals versus the fitted values (i.e.
 checking the normality assumption and constant variance assumption of the model
 respectively) to gain confidence that the model assumptions are reasonable.
- If there are any departures from the distributional assumptions, alternative models will be explored using appropriate transformed data.

Model Results Presentation

- Geometric least-squares means for each treatment, point estimates and associated 90% confidence intervals for the ratios for each parameter will be produced in tabular format.
 Estimates of within-subject variability (%CVw) will also be provided. %CVw represents a pooled measure of within-subject variability across all treatments.
- Comparative plots of individual Accumulation Ratio will be generated by dose group on linear and semi-logarithmic scales.
- The accumulation ratio will be listed and summarized along with other PK parameters.
- Supportive SAS output from statistical analysis will be generated.

Subgroup Analyses

Not applicable

Sensitivity and Supportive Analyses

Not applicable

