10.1. Sample Size Determination

Sample sizes are based on prior relative bioavailability studies with GSK2838232 and take into account variability and logistical factors while no formal calculation of power or sample size for Parts 1 or 2 of the study was performed. A sample size of approximately 16 participants for Part 1 and 10 participants for Part 2, considering a drop-out rate of 25%, of the study should be sufficient to provide useful estimates of inter-participant variability for GSK2838232 PK parameters and safety assessments.

Additional participants will be randomized and enrolled to ensure a minimum of 12 evaluable participants for Part 1 (crossover of tablet and capsule) and 8 evaluable participants for Part 2 (6 active: 2 placebo).

Sample size assumptions

For Part 1 of the study: The between-subject variability (%CVb) for AUC(0- ∞), and Cmax parameters from previous studies at different doses were 21% to 47% and 41% to 44%, respectively. Assuming within-subject variability (%CVw) for AUC(0- ∞) and Cmax is 80% of highest between-subject variability (which will be 38% and 35%, respectively), and with the sample size of 12, it is estimated that the precision (i.e., half

width of the 90% confidence interval on the log scale) for the relative bioavailability assessment will be within 31.7% of the point estimate for AUC($0-\infty$), and within 29.0% of the point estimate for Cmax. If the point estimate of the ratio of geometric mean for Cmax is 1, then 90% confidence interval will be approximately (0.78, 1.29).

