Part 2 of this study is designed to assess time to steady-state of GSK2838232 when administered as non-boosted once-daily doses of a tablet formulation for 11 days. No formal hypothesis will be tested. Mean plasma GSK2838232 pre-dose values between Days 2 through 11 and $C\tau$ of Day 11 will be plotted against time. Achievement of plasma GSK2838232 steady-state will be assessed by calculating the 90% CI of the slope of the linear regression of log $(C\tau)$ versus time. The dependent variable in the linear regression model will be log $(C\tau)$ and the model will include a random intercept effect for participant and a fixed slope effect for study day. Steady state will be reached if the 90% CI for the slope estimate includes zero.

Part 2 Accumulation

Part 2 of this study is designed to assess accumulation of GSK2838232 when administered as non-boosted once-daily doses of a tablet formulation for 11 days. No formal hypothesis will be tested. The extent of accumulation of GSK2838232 will be

evaluated by comparing AUC(0- τ), Cmax and C τ between Day 11 and Day 1. For each of these comparisons an analysis of variance will be conducted on the log scale. The difference between Day 11 and Day 1 least square (LS) means and a 90% CI will be computed by fitting a mixed effects model with the log-transformed PK parameter as the dependent variable, day as a fixed effect and participant as a random effect. The estimated difference and confidence interval obtained on the log-scale will be exponentiated to provide an estimate of the Day 11 to Day 1 ratio and its associated 90% CI. If the model fails to converge, participants will be fit as a fixed effect.

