All the derived parameters described above will be listed. For each of these parameters, except tmax and tlag, the following summary statistics will be calculated for each treatment group: N, n, arithmetic mean, standard deviation (SD), median, minimum, maximum, geometric mean with associated 95% CI, standard deviation of logarithmically transformed data, and the between-participant CV (%CVb) based on the geometric mean for the loge-transformed PK parameters. For tmax and tlag, N, n,median, maximum, minimum, arithmetic mean and standard deviation will be calculated.

As per final RAP Section 9.2.5, statistical methodology section of Part 2 Steady State Assessment, end point or variable is given as GSK2838232 pre-dose values between Days 2 through 11, however it should be GSK2838232 pre-dose values between Days 3 through 11.

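### The steady-state model in SAP 9.2.5 cannot be estimated: an unstructured 9-day covariance matrix with 6 active participants gives a likelihood that has no maximum

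*SAP*

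**What the plan says.** Protocol section 10.4.2.3 and SAP section 2.4 describe a regression of log pre-dose concentration on day, in which "the model will include a random intercept effect for participant and a fixed slope effect for study day". SAP section 9.2.5 repeats this model and adds, under model checking:

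- Covariance: "An unstructured covariance structure for the R matrix will be used", through type=UN on the REPEATED statement.
- Fallback if the model does not converge: "alternative correlation structures may be considered such as CSH or CS".
- AIC "will be used to assist with the selection of covariance structure".
- Degrees of freedom: "The Kenward and Roger method for approximating the denominator degrees of freedom".

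Steady state is concluded if the "slope estimate is close to zero or the 90% CI for the slope estimate includes zero". No sensitivity analysis is planned. The original analysis days were 2 to 11. SAP Addendum section 2.9 changes them ("however it should be GSK2838232 pre-dose values between Days 3 through 11") and leaves the covariance specification as it was. Protocol section 10.1 plans 8 evaluable participants in Part 2, 6 on active drug and 2 on placebo.

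**The concern.** An unstructured covariance matrix needs more participants than time points, and here there are fewer. The random intercept is also redundant beside it, because an unstructured matrix already contains any common between-participant variance.

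The decision rule uses the 90% CI for the slope. Two outcomes are possible. If a near-singular fit is accepted, the CI has no sound basis and is likely to be too narrow, so zero would be wrongly excluded and steady state not declared by that route. If the fit is rejected, the covariance structure is picked after the data are seen. AIC cannot guide that choice fairly, because one candidate has an unbounded likelihood.

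**Working it through.** The documents give no figure for the covariance model itself, so there is none to reproduce.

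**Inputs**
- Active participants: 6 (Protocol 10.1). Placebo participants have no drug concentration to log-transform. Protocol 5.2 enrols 10; at 6:2 that is 10 × 6/8 = 7.5, so at most 7 or 8 active (assuming the ratio is kept).
- Days: 3 to 11, so p = 9 (SAP Addendum 2.9).
- Fixed effects: 2 (intercept and slope).

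**Parameter count.** Unstructured: 9 × 10/2 = 45, for 6 × 9 = 54 troughs. The random-intercept model has 2.

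**Why there is no maximum.** At any fixed slope, n residual vectors span at most n of the 9 dimensions. In the other 9 − n dimensions the variances can be cut without increasing the quadratic form, while −(n/2)·log|R| rises. The ML gain per 100-fold cut is n(9 − n)·ln(100)/2, with ln(100)/2 = 2.303. REML gives back 2.303 for each fixed effect that becomes exactly determined in those dimensions, at most min(2, 9 − n).

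| Active n | ML gain per cut | REML gain per cut (limit) |
|---|---|---|
| 6 | 6 × 3 × 2.303 = 41.4 | 41.4 − 2 × 2.303 = 36.8 |
| 7 | 7 × 2 × 2.303 = 32.2 | 32.2 − 2 × 2.303 = 27.6 |
| 8 | 8 × 1 × 2.303 = 18.4 | 18.4 − 1 × 2.303 = 16.1 |

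**Numerical check.** On simulated data (6 participants, 9 days), setting the free variances to 1e-2, 1e-4, 1e-6 and 1e-8 gave ML log-likelihoods of 46.8, 87.0, 128.1 and 169.5, and REML values of 40.5, 78.6, 115.3 and 152.2. The gains were the same with the slope fixed at −0.10, 0, 0.03 or 0.10 per day, so the likelihood does not determine the slope. With 10 participants the values stayed at 67.5 (ML) and 60.7 (REML). A finite maximum needs at least p + 1 participants, here 10 on active drug.

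**AIC.** The penalty for 43 extra parameters is 2 × 43 = 86. Two cuts at n = 6 lower −2logL by 2 × 2 × 41.4 = 166 (ML) or about 147 (REML), so the unstructured matrix can be made to win.

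**Redundancy in the fallback.** With residual variance 0.02, an intercept variance of 0.05 plus a CS covariance of 0.07 gave the same REML value (18.3147) as 0.12 plus 0. CS and a separate random intercept cannot both be estimated.

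**Direction of error.** In 300 simulated datasets with true slope 0 (participant SD 0.35 and residual SD 0.2, both assumed), unstructured REML fits were stopped at 20, 50 and 150 iterations. The median slope SE was 0.33, 0.10 and 0.09 of the random-intercept SE. The 90% CI (t with 5 df) excluded zero in 73%, 87% and 84% of datasets, against 11% for the random-intercept model. Every unstructured run was flagged as not converged and no Kenward-Roger adjustment was applied, so these figures show direction only.

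**The simpler model.** Random intercept with independent residuals has a finite maximum on the data of the numerical check (ML 24.4, REML 19.0). With a sum of squared day deviations of 60 and 54 − 6 − 1 = 47 df, the 90% CI half-width is t(0.95, 47) × σ/√(6 × 60). This gives 0.0088, 0.0177 and 0.0354 per day for assumed residual SD 0.10, 0.20 and 0.40.

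**The case against.** The strongest reply is that the plan already copes. Non-convergence triggers a named fallback, CS is close to the structure recommended here, and the simulated harm comes from fits that were all flagged as not converged, which is the plan's own trigger. That is fair as to consequence: the analysis can still be run, and it is not known whether the trial's software would flag the fit. It does not repair the text. The fallback is optional and open-ended, does not cover a near-singular fit reported as converged, and leans on an AIC that cannot rank the unstructured matrix.

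A second point is that the table shell for this analysis (SAP Appendix 13, Non-Standard4) also shows shorter windows. By the p + 1 condition, the unstructured matrix would be estimable for Days 6–11 with 7 active participants, and for Days 5–11 and 6–11 with 8. With the planned 6 it fails in all four windows shown.

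A third is that the replacement also under-covers when troughs are serially correlated. This stands, and it is why a sensitivity analysis is needed. Finally, the impact is low: the endpoint is secondary, the analysis descriptive, a slope near zero is a separate route to the conclusion, and plots and a SAS output listing (listing 74 in the Addendum) allow review. This limits the importance of the point but does not remove it.

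**Conclusion.** The concern holds. With 6, 7 or 8 active participants over Days 3 to 11, the model written in SAP 9.2.5 has no likelihood maximum, so it yields no defined slope or CI. This is algebra and does not depend on the assumed variances. What the study would actually report is less certain, since it depends on how the software treats a singular fit and on an optional fallback. The likely direction, a CI that is too narrow and excludes zero too often, rests on simulation under assumed variances. The consequence is confined to the steady-state conclusion. The SAP should be corrected, but no primary endpoint is affected.

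**What to change.** In SAP 9.2.5:

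1. Delete the unstructured-matrix bullet and the AIC bullet.
2. Replace the CSH/CS bullet with one mandatory structure: the random participant intercept already named in both documents, with independent residuals, keeping Kenward-Roger. R = CS without a separate random intercept is equivalent when the common covariance is not negative.
3. State that independent residuals are an SAP choice, because Protocol 10.4.2.3 names neither a residual structure nor a df method.
4. Under sensitivity analyses, add the mean of per-participant slopes with a t-interval on active participants minus 1 df (5 df for 6). Say in advance that the rule is applied to the random-intercept CI and that any disagreement will be reported.
5. If the change follows database lock, record that in the addendum or study report.

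The cost is SAP wording and simpler code. The trade-off should be stated. Under assumed values (residual SD 0.2, 6 participants, Days 3–11), the nominal 90% random-intercept CI covers 84.0%, 80.5%, 72.5% and 64.1% at AR(1) correlation 0.2, 0.3, 0.5 and 0.7. It covers 88%, 82% and 75% when individual slopes vary with SD 0.01, 0.02 and 0.03 per day. The per-participant t-interval stays at 90% throughout, but it is wider and so includes zero more readily under the plan's rule. At a true slope of 0.03 per day it includes zero in 21% of trials against 12% (no serial correlation), and in 43% against 15% (correlation 0.5). With complete data both methods give the same slope estimate; only the CI differs.

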9.3 Exploratory Pharmacokinetic Analyses

Not applicable.

10. POPULATION PHARMACOKINETIC (POPPK) ANALYSES

Not applicable.

11. PHARMACODYNAMIC ANALYSES

Not applicable.

12. PHARMACOKINETIC / PHARMACODYNAMIC ANALYSES

Not applicable.

14. APPENDICES

14.1 Appendix 1: Protocol Deviation Management and Definitions for Per Protocol Population

14.2.1 Exclusions from Per Protocol Population

Not applicable.

14.2 Appendix 2: Schedule of Activities

14.2.1 Protocol Defined Schedule of Events

Schedule of Assessments for Part 1A and Part 1B: Single Dose RBA \pm Food

	Screening (within 30 days of	in 30 days of													
Procedure	Day 1 - carried out over multiple days – except as noted in	Day -3	Day -2	Day -1	Day 1	Day 2	Day 3	Day 4	Day 5	Day 6	Day 7	7-14 days			
	footnotes)					24 h	48 h	72 h	96 h	120 h					
Admission to Unit		X2													
Outpatient Visit	Χ											X			
Informed Consent	Χ														
Medical/medication/															
drug/alcohol history	Χ														
(Demographics)															
Full Physical Examination	Х														
Brief Physical Examination			Х				X					X			
Height, Weight, BMI	Χ														
Inclusion/Exclusion	Χ														
Vital signs ³	Χ		X	X	X	X	Χ	Χ				X			
12 Lead ECG ⁴	Χ		Х	Χ	Х	Χ	Χ					Х			
Echocardiogram ⁵	Χ														
Drug/alcohol/cotinine screen	Χ	Χ													
HbsAg, HCV, HIV tests	Χ														
Hem/Chem/Urine tests ⁶	Χ		Х	Х		Х		Х				Х			
Serum FSH (as appropriate)	Χ														
Troponin I ⁷	Χ			X	Χ	Χ		X							
24 h Holter Monitoring ⁸	Χ														
Pregnancy test (women)	Χ	Χ										Χ			
Run-in Dosing with RTV			Х	Х											
Dosing with GSK2838232+RTV					X										

	Screening (within 30 days of	Periods 1	Periods 1 through 3											
Procedure	Day 1 - carried out over multiple days – except as noted in	Day -3	Day -2	Day -1	Day 1	Day 2	Day 3	Day 4	Day 5	Day 6	Day 7	7-14 days		
	footnotes)					24 h	48 h	72 h	96 h	120 h				
PK Sampling ⁹					X	Χ	Х	Χ	Χ	Χ				
Adverse Event Review ¹⁰				Х	Χ	Х	Х	Х	Х	Х	Х	Х		
Con Med Review			Х	Х	Χ	Χ	Х	Χ	Х	Χ	Χ	Χ		
Discharge from Unit ¹¹						Х								
Out Patient Visit							Х	Χ	Х	Χ	Χ			

205820

BMI = Body Mass Index; ECG = Electrocardiogram; FSH = Follicle Stimulating; HbsAg = Hepatitis B surface Antigen; HCV = Hepatitis C Virus; HIV = Human Immunodeficiency Virus; Hem/Chem = Hematology/Clinical Chemistry; RTV = Ritonavir; PK = Pharmacokinetic(s); Con Med = Concomitant medications.

- 1. Follow-up Visit to take place after Treatment Period 2.
- 2. When participants stay in the unit across treatment periods, drug/alcohol/cotinine screen and pregnancy test (women) are not required on Day -3 for later periods.
- 3. On Day 1, Blood pressure (BP) and Heart rate (HR) will be collected at pre-dose (triplicate) and single assessments at 1, 2, 4, 6, 8, 12, 24, 48, and 72 h post-dose.
- 4. On Day 1, 12-lead ECG will be collected at pre-dose (triplicate), and single assessments at 1, 2, 4, 6, 8, 12, 24, 48 and 72 h post-dose.
- 5. Echocardiograms must be within 100 days of Day 1.
- 6. Samples for Chemistry and Hematology: Blood samples will be obtained after an 8-hour fast.
- 7. Collect one troponin sample to be analyzed at local laboratory. A second sample will be collected, frozen and stored on site for potential high sensitivity troponin analysis.
- 8. 24-h Holter monitoring to be performed after confirming negative urine drug screen at screening, and must be within 30 days of Day 1. Holter monitoring on other days only if needed.
- 9. Plasma PK samples for bioanalysis for GSK2838232 will be collected pre-dose (within 15 minutes prior to dosing) and 0.5, 1, 1.5, 2, 2.5, 3, 3.5, 4, 6, 8, 12, 24, 36, 48, 72, 96, and 120 h post-dose. Samples will be acidified with an equal volume of 50 mmol citrate acid buffer pH 4.0.
- 10. An AE enquiry will be made at each visit, participants will be asked if they have experienced any neuropsychiatric adverse events, including psychosis or altered mental status. (see guidance for grading Altered Mental Status in Appendix 4).
- 11. Participants may be discharged after all study procedures are completed. Participants will be in house for PK blood samples on Day 3 (48 h), Day 4 (72 h), Day 5 (96 h) and Day 6 (120 h) of both study periods.

Schedule of Assessments for Part 2: Repeated Doses for 11 days:

Measurement	Screening (within 30 days of Day 1 - carried out over																		Follow- up
Measurement	multiple days	Day –1	Day 1	Day 2	Day 3	Day 4	Day 5	Day 6	Day 7	Day 8	Day 9	Day 10	Day 11 0 h	Day 12 24 h	Day 13 48 h	Day 14 72 h	Day 15 96 h	Day 16 120 h	7-14 days after last dose
Admission to Unit		Χ																	
Informed Consent	X																		
Medical/medication/ drug/alcohol history (Demographics)	X																		
Full Physical Examination	Х													Х					
Brief Physical Examination		Х																	Х
Height, Weight, BMI	X																		
Inclusion/Exclusion	X																		
Medical History	X																		
Vital Signs ¹	Х	Χ	Χ	Χ	Χ	Χ	Χ	Χ	Χ	Χ	Χ	Χ	Χ	Χ	Χ	Χ			Χ
12-lead ECG ²	X	Χ	Χ	Χ	Χ		Х			Х			X	X					Χ
Echocardiogram ³	X																		
Drug/alcohol/ /cotinine Screen	X	Х																	
HbsAg, HCV, HIV Testing	Х																		
Hem/Chem tests ⁴	Х	Χ		Х		Х		Х		Х			Χ			Х			Χ
Urinalysis	Х	Χ		Χ		Χ							Х			Х			Χ
Serum FSH (as appropriate)	Х																		
Troponin I ⁵	Х	Χ	Χ	Χ			Х			Х			Х			Х			

	Screening (within 30 days of Day 1 - carried																		Follow- up
Measurement	out over multiple days - except as noted in footnotes)	Day -1	Day 1	Day 2	Day 3	Day 4	Day 5	Day 6	Day 7	Day 8	Day 9	Day 10	Day 11 0 h	Day 12 24 h	Day 13 48 h	Day 14 72 h	Day 15 96 h	Day 16 120 h	7-14 days after last dose
24 h Holter Monitoring ⁶	Х																		
Pregnancy Test (females)	Х	Х																	Х
Dosing of GSK2838232			Χ	Χ	Х	Χ	Х	Х	Χ	Χ	Х	Χ	Х						
Plasma PK sampling ⁷			Х	Χ	Χ	Χ	Х	Х	Χ	Χ	Х	Χ	Χ	Χ	Χ	Χ	Х	Χ	
Adverse Event Assessment ⁸		Х	Х	Х	Х	Х	Х	Х	Х	Х	Х	Х	Х	Х	Х	Х	Х	Х	Х
Concomitant Medications		Х	Х	Х	Х	Х	Х	Х	Х	Х	Х	Х	Х	Х	Х	Х	Х	Х	Х
Discharge from Unit															X ⁹				
Out Patient Visit	Х															Χ	Χ	Χ	Х

BMI = Body Mass Index; ECG = Electrocardiogram; FSH = Follicle Stimulating Hormone; HbsAg = Hepatitis B surface Antigen; HCV = Hepatitis C Virus; Hem/Chem = Hematology/Clinical Chemistry; HIV = Human Immunodeficiency Virus; IP = Investigational Product; PK = Pharmacokinetic(s).

- 1. A single blood pressure (BP) and Heart rate (HR) assessment will be collected at screening and Day -1. On Day 1 triplicate BP and HR will be collected at pre-dose and single assessments at 1, 4, 24, 48 and 72 h (Day 4) post-dose, Day 5, Day 6, Day 7, Day 8, Day 9, Day 10, Day 11 at pre-dose (triplicate), and single assessment at 1, 4, 24, 48 and 72 h post-dose, and at follow-up.
- 2. A single 12-Lead ECG will be collected at screening and Day -1. On Day 1 triplicate 12-Lead ECGs will be collected at pre-dose, and then single 12-Lead ECGs at 1, 4 and 12 h post-dose. Single 12-Lead ECGs will be collected on Days 2, 3, 5, 8. On Day 11 triplicate 12-Lead ECGs will be collected pre-dose, and then single 12-Lead ECGs collected at 1, 4, 12 and 24 h post-dose and at follow-up.
- 3. Echocardiograms must be within 100 days of Day 1.
- 4. Samples for Chemistry and Hematology: Blood samples will be obtained after an 8-hour fast.
- 5. Collect one troponin sample to be analyzed at local laboratory. A second sample will be collected and frozen for potential high sensitivity troponin analysis.
- 6. 24-h Holter monitoring to be performed after confirming negative urine drug screen at screening, and must be within 30 days of Day 1. Holter monitoring on other days only if needed.

- 7. Plasma PK samples for GSK2838232 will be collected as follows: Day 1; pre-dose (within 15 minutes prior to dosing) and 0.5,1, 1.5, 2, 2.5, 3, 3.5, 4, 6, 8, 12 and 24 h post-dose (prior to Day 2 dose). Days 3 to 10 pre-dose (within 15 minutes prior to dosing). Day 11; pre-dose (within 15 minutes prior to dosing) and 0.5, 1, 1.5, 2, 2.5, 3, 3.5, 4, 6, 8, 12, 24, 36, 48, 72, 96 and 120 h post-dose. Samples will be acidified with an equal volume of 50 mmol citrate acid buffer pH 4.0.
- 8. An AE enquiry will be made at each visit, participants will be asked if they have experienced any neuropsychiatric adverse events, including psychosis or altered mental status. (see guidance for grading Altered Mental Status in Appendix 4).
- 9. Participants will be discharged after all study procedures are completed on the morning of Day 13 (after the 48 h post-final dose sample time point) with instructions to return fasted on the mornings of Day 14 for 72 h PK sample, Day 15 for 96 h PK sample, and Day 16 for 120 h PK sample

2017N322544_01 **CONFIDENTIAL**

